### **6.6.2. Dose Modification Criteria for RMC-4630 and Cobimetinib**

In general, dose adjustments should be based on attribution to a particular drug, if known. Certain adverse events are known to be associated with administration of cobimetinib (cobimetinib IB) whereas others have been observed with the administration of RMC-4630 in clinical or preclinical studies (RMC-4630 IB). [REDACTED]

The following principles apply to Dose Escalation component of the study and should be employed for Grade 3 and certain Grade 4 AEs.

- If the AE is a known toxicity of cobimetinib only, cobimetinib should be interrupted and then dose reduced one level if recovery to  $\leq$ Grade 1 occurs within 28 days. RMC-4630 should be continued at the same dose. However, at the investigator’s discretion, RMC-4630 may be held if the AE does not improve with holding cobimetinib. If the AE does not resolve within 28 days from onset, permanently discontinue cobimetinib.
- If the AE is suspected to be due to RMC-4630, RMC-4630 should be interrupted and then dose reduced one level if recovery to  $\leq$ Grade 1 occurs within 28 days. Cobimetinib should be continued at the same dose. However, at the investigator’s discretion, cobimetinib may be held if the AE does not improve with holding RMC-4630. If the AE does not resolve within 28 days from onset, permanently discontinue RMC-4630.
- If the AE is known for both drugs, hold both drugs until recovery to  $\leq$ Grade 1. Restart at a reduced dose of the drug that was last escalated by one dose level if the recovery to Grade  $<1$  is within 28 days. The second drug may also be dose reduced by one level at the investigator’s discretion and after discussion with the sponsor Medical Monitor.
- If the AE is unknown for either drug, hold both drugs until recovery to  $\leq$ Grade 1. Restart at a reduced the dose of the drug that was last escalated by one dose level if the recovery to grade  $<1$  is within 28 days. The second drug may also be dose reduced by one level at the investigator’s discretion and after discussion with the sponsor Medical Monitor.

**Dose escalation-** If more than 2 dose reductions are required of cobimetinib, then permanently discontinue cobimetinib. RMC-4630 may be continued as monotherapy provided that the participant is benefitting from treatment with no evidence of disease progression. If RMC-4630 is continued as a single agent, please refer to specific guidelines provided at the bottom of this section. If more than 2 dose reductions of RMC-4630 are required, permanently discontinue both drugs.

**Final expansion at RP2DS (Refer to [Table 11](#))**

- [REDACTED]
- There are no dose reductions permitted for cobimetinib. If dose reduction for cobimetinib is required, then permanently discontinue cobimetinib.

RMC-4630 may be continued as monotherapy provided that the participant is clinically benefitting from treatment with no evidence of disease progression. [REDACTED]

[REDACTED]

[REDACTED] Guidelines in [Table 9](#) mainly pertain to the dose escalation phase of the study. The investigator or treating physician should use his/her best medical judgement for management.

General guidance for dose modification during final dose expansion is shown in [Table 10](#).

**Table 9      Dose Modification Guidelines for RMC-4630 and Cobimetinib**

[REDACTED]	[REDACTED]
[REDACTED]	[REDACTED]
[REDACTED]	[REDACTED]
[REDACTED]	[REDACTED]
[REDACTED]	[REDACTED]

[REDACTED]	[REDACTED]
[REDACTED]	[REDACTED]
[REDACTED]	[REDACTED]
[REDACTED]	[REDACTED]

[REDACTED]	[REDACTED]
[REDACTED]	[REDACTED]
[REDACTED]	[REDACTED]
[REDACTED]	[REDACTED]

Dose modifications may also occur following the first cycle (DLT assessment period) during the Dose-Escalation Component or Dose-Expansion Component (where applicable) in the following specific instances:

- Any participant who experiences a Grade 3 AE that constitutes a DLT may be considered for dose reduction to last dose cohort upon recovery of the AE to Grade 1 or baseline if deemed medically appropriate by the investigator and Medical Monitor. These participants will be considered to have experienced a DLT at the original dose and, therefore, will not be permitted to remain at the same dose.
  - For participants in the Final Expansion Cohort – if an AE/SAE occurs within the first cycle and meets the DLT definition, participant may dose reduce RMC-4630 to 100 mg D1D2.
- Any participant who experiences a < Grade 3 AE that does not constitute a DLT but that recurs more than once ( $\geq$  Grade 2) after recovering from the initial onset of the AE may be considered for a dose reduction upon recovery of the AE to Grade 1 or baseline if deemed medically appropriate by the investigator and sponsor Medical Monitor. Discontinuation of the study medications after third occurrence of the AE that is Grade 2 (intolerable) or Grade 3.
- Re-challenge at the same or lower dose may be considered after resolution of treatment-related or treatment-unrelated AEs provided the AE did not meet DLT criteria. If the AE recurs, dose modification may be considered.
- Continuation of a single agent RMC-4630 may be allowed if there is presence of, or potential for, clinical benefit as assessed by the investigator and sponsor Medical Monitor. The dose and schedule of RMC-4630 may be cross-referenced to the on-going monotherapy study RMC-4630-01. The options are:

**Dose Escalation:**

■	[REDACTED]
■	[REDACTED]
–	[REDACTED]
–	[REDACTED]
–	[REDACTED]
–	[REDACTED]
–	[REDACTED]

**Final Expansion at RP2DS:**

[Redacted]

**Table 11 RMC-4630 and Cobimetinib Dose Levels (Final Expansion at RP2DS)**

[Redacted]	[Redacted]	[Redacted]
[Redacted]	[Redacted]	[Redacted]
[Redacted]	[Redacted]	[Redacted]
[Redacted]	[Redacted]	[Redacted]

**6.6.3. Dose Modification Criteria for RMC-4630 and Osimertinib (Study in US Only)**

In general, dose adjustments should be based on attribution to a particular drug, if known.

[Redacted]

[Redacted]

- [Redacted]

If more than 1 dose reduction is required of osimertinib, then permanently discontinue osimertinib (please see [Table 12](#)). RMC-4630 may be continued as monotherapy provided that the participant is benefiting from treatment with no evidence of disease progression ([Table 13](#)). If more than 2 dose reductions of RMC-4630 are required, permanently discontinue both drugs.

**Table 12 Osimertinib Dose Levels**

[REDACTED]
[REDACTED]
[REDACTED]
[REDACTED]

**Table 13 RMC-4630 Dose Levels (Dose Escalation)**

[REDACTED]	[REDACTED]
[REDACTED]	[REDACTED]
[REDACTED]	[REDACTED]
[REDACTED]	[REDACTED]
[REDACTED]	[REDACTED]
[REDACTED]	[REDACTED]

Actual dose levels during dose escalation may be different as intermediate dose levels of RMC could be explored per Dose Committee decision.

General guidance and dose modification guidelines for a subset of common AEs seen with osimertinib or other inhibitors of the RAS-MAPK pathway are shown in [Table 14](#) below. The investigator or treating physician should use his/her best medical judgement for management.

**Table 14 Dose Modification Guidelines for RMC-4630 and Osimertinib**

AE	Action
[REDACTED]	[REDACTED]
[REDACTED]	[REDACTED]
[REDACTED]	[REDACTED]

[Redacted]	
[Redacted]	
[Redacted]	[Redacted]
[Redacted]	[Redacted]
[Redacted]	[Redacted]
[Redacted]	[Redacted]
[Redacted]	[Redacted]

at the original dose and schedule and, therefore, will not be permitted to remain at the same dose and schedule.

- Re-challenge at the same or lower dose may be considered after resolution of treatment-related or treatment-unrelated AEs provided the AE did not meet DLT criteria. If the AE recurs, dose modification may be considered.
- If both drugs have been on hold for a treatment related AE, a staggered re-challenge strategy may be considered by re-starting either RMC-4630 or osimertinib first followed by the second agent a week later. This strategy might minimize the risk of recurrence of the AE which led to dose interruption and may help understand which drug may be driving the toxicity.
- Continuation of RMC-4630 alone may be allowed if there is presence of clinical benefit as assessed by the investigator and sponsor Medical Monitor.

**6.6.4. Supportive Care Guidelines for Selected Expected Toxicities**

Please refer to [Table 9](#) for dose modification guidelines for RMC-4630 and cobimetinib or [Table 14](#) for RMC-4630 and osimertinib. [REDACTED]

[REDACTED]

The investigator or treating physician should use his/her best medical judgement for management. Published guidelines are available for MEK, BRAF and RTK inhibitors ([Califano 2015](#), [Welch 2015](#), [Daud 2017](#)) and guidelines for selected toxicities are summarized below.

**6.6.4.1. [REDACTED]**

[REDACTED]

[REDACTED]

[REDACTED]

[Redacted]

**6.6.4.2.** [Redacted]

[Redacted]

[Redacted]

[Redacted]

[Redacted]

[Redacted]

**6.6.4.3.** [Redacted]

[Redacted]

[Redacted]

[Redacted]

[Redacted]

[Redacted text block]

[Redacted text block]

**6.6.4.4.** [Redacted]

[Redacted text block]

[Redacted text block]

**6.6.4.5.** [Redacted]

[Redacted text block]

[Redacted text block]

**6.6.4.6.** [Redacted]

[Redacted text block]

[Redacted text block]

**6.6.4.7.** [Redacted]

[Redacted]

[Redacted]

[Redacted]

[Redacted]

**6.6.4.8.** [Redacted]

[Redacted]

**6.6.4.9.** [Redacted]

[Redacted]

[Redacted]

[Redacted]

6.6.4.10. [REDACTED]

[REDACTED]

6.6.4.11. [REDACTED]

[REDACTED]

6.6.4.12. [REDACTED]

[REDACTED]

6.6.4.13. [REDACTED]

[REDACTED]

**6.7. Intervention after the End of the Study**

Participants who continue to receive study intervention at the end of the study and are considered to be deriving clinical benefit from RMC-4630 and cobimetinib or RMC-4630 and osimertinib will be considered for enrollment in a separate extended use or roll-over study.

## 7. DISCONTINUATION OF STUDY INTERVENTION AND PARTICIPANT DISCONTINUATION/WITHDRAWAL

### 7.1. Discontinuation of Study Intervention

In some instances, it may be necessary for a participant to permanently discontinue study intervention. Refer to the SoA ([Section 1.3](#)) for data to be collected at the time of discontinuation of study intervention.

Participants may stop study therapy yet continue to be monitored in the study under the following circumstances:

- A participant who experiences a Grade 4 AE, including those that meet the criteria of a DLT (ie, during C1), but is deemed by the investigator not to meet the criteria for withdrawal from the study ([Section 7.2](#)).
- Prolonged QTcF (defined as QTc using Fridericia's formula [QTcF] >500 msec **OR** change from baseline of QTcF >60 msec) and that does not resolve after excluding other causes

A participant must be discontinued from protocol-prescribed therapy and removed from the study if any of the following apply:

- Documented disease progression based on RECIST v1.1
  - In certain circumstances (eg, an isolated site of progression with responses at other sites that may be amenable to localized radiotherapy), participants may be allowed to continue therapy during and after radiation with approval from sponsor Medical Monitor.
- Significant adverse events leading to discontinuation of study medications (report on adverse event eCRF) ([Section 6.6](#))
- Death
- Participant's request to withdraw from study treatment or withdraw consent
- Ineligibility
- Unwillingness or inability to comply with study requirements
- Initiation of alternative anticancer therapy
- Investigator's decision
  - Clinical need for concomitant or other ancillary therapy that is not permitted in the study
  - Unrelated intercurrent illness that, in the judgment of the investigator, will affect assessments of clinical status to a significant degree

- Investigator believes that it is in the best interest of the participant to withdraw from the study
- Pregnancy
- Lost to follow-up
- Sponsor's decision to terminate the study

Participants who have stable disease as best response will be allowed to continue on treatment provided the investigator believes it is in the participant's best interest and none of the above criteria have been met.

Participants who discontinue study treatment should complete the safety follow-up or EOT visit, within 30 days after the last treatment dose. Participants who do not withdraw consent will also undergo long-term follow-up until death or end of study or lost to follow-up. See [Section 7.2](#) for details on study discontinuation.

## **7.2. Participant Discontinuation/Withdrawal from the Study**

A participant may withdraw from the study at any time at his/her own request or may be withdrawn at any time at the discretion of the investigator for safety, behavioral, compliance, or administrative reasons. This is expected to be uncommon.

A participant may be withdrawn from the study for any of the following reasons:

- Participant's withdrawal of consent for participation in the study
- Sponsor's decision to terminate the study
- Participant is lost to follow-up
- Death

If study discontinuation occurs at the same time as treatment discontinuation, every effort should be made to complete the safety follow-up or EOT visit, within 30 days after the last treatment dose. Participants who do not withdraw consent will also undergo a long-term follow-up for survival (SoA in [Section 1.3](#)).

If the participant withdraws consent for disclosure of future information, the Sponsor may retain and continue to use any data collected before such a withdrawal of consent.

If a participant withdraws from the study, he/she may request in writing destruction of any samples taken and not tested, and the investigator must document this in the site study records.

### 7.3. Lost to Follow-Up

A participant will be considered lost to follow-up if he/she repeatedly fails to return for scheduled visits and is unable to be contacted by the study site.

The following actions must be taken if a participant fails to return to the clinic for a required study visit:

- The site must attempt to contact the participant and reschedule the missed visit as soon as possible and counsel the participant on the importance of maintaining the assigned visit schedule and ascertain whether or not the participant wishes to and/or should continue in the study.
- Before a participant is deemed lost to follow-up, the investigator or designee must make every effort to regain contact with the participant (where possible, 3 telephone calls and, if necessary, a certified letter to the participant's last known mailing address or local equivalent methods). These contact attempts should be documented in the participant's medical record.
- Should the participant continue to be unreachable, he/she will be considered to have withdrawn from the study.

Discontinuation of specific sites or of the study as a whole are handled as part of [Appendix 1](#).

## 8. STUDY ASSESSMENTS AND PROCEDURES

- Study procedures and their timing are summarized in the SoA ([Section 1.3](#)). Protocol waivers or exemptions are not allowed.
- Immediate safety concerns should be discussed with the Sponsor immediately upon occurrence or awareness to determine if the participant should continue or discontinue study intervention.
- Adherence to the study design requirements, including those specified in the SoA, is essential and required for study conduct.
- All screening evaluations must be completed and reviewed to confirm that potential participants meet all eligibility criteria. The investigator will maintain a screening log to record details of all participants screened and to confirm eligibility or record reasons for screening failure, as applicable.
- Procedures conducted as part of the participant's routine clinical management (e.g. blood count) and obtained before signing of the ICF may be used for screening or baseline purposes provided the procedures met the protocol-specified criteria and were performed within the time frame defined in the SoA.

- The maximum amount of blood collected from each participant over a 12-cycle duration of the study, including any extra assessments that may be required, will not exceed 0.9 L. Repeat or unscheduled samples may be taken for safety reasons or for technical issues with the samples.

## 8.1. Efficacy Assessments

Participants will be assessed for response using RECIST v1.1 ([Appendix 6](#)) as assessed by the investigator. All measurable disease must be documented at screening and reassessed at each subsequent tumor evaluation. Measurable disease is not required in the Dose-Escalation Component; however, disease must be evaluable by other measures and documented accordingly. Response assessments will be assessed by the investigator based on physical examination (including measurement of cutaneous lesions) and CT scans or MRI. Imaging should include chest and abdomen (neck and pelvis are to be included depending on primary tumor type and investigator assessment). At the investigator's discretion, the imaging studies may be repeated at any time if disease progression is suspected. Additional studies, such as positron emission tomography (PET) scans, should be performed if clinically indicated. Care should be taken to repeat the same modality used at screening throughout the study and to ensure all anatomy imaged at screening is again imaged at follow-up scans for any given participant. As part of the tumor assessment, physical examinations should include all areas of tumor involvement that are amenable to examination, including biopsy sites, lymph nodes, and bone tenderness, if applicable.

All imaging studies should be evaluated by a local radiologist with expertise in the imaging modality. The investigator is responsible for determining the overall response at each timepoint.

The first response assessment will occur after completion of C2 (C3D1  $\pm$  7 days). Subsequent response assessments will occur every 2 cycles through the end of C6 (C7D1  $\pm$  7 days) and then every 3 cycles.

## 8.2. Safety Assessments

Planned timepoints for all safety assessments are provided in the SoA ([Section 1.3](#)).

### 8.2.1. Physical Examinations

- A complete physical examination will include, at a minimum, assessments of the head, eyes, ears, nose, and throat (HEENT), dermatologic, cardiovascular, respiratory, GI, lymphatic, musculoskeletal, and neurological systems. Height and weight will also be measured and recorded. A symptom/AE-directed physical examination should be performed as indicated by participant presentation or participant reported symptoms.

- A limited examination should include an evaluation of the HEENT, dermatologic, cardiovascular, respiratory, and GI systems. A symptom/AE-directed physical examination should be performed as indicated by participant presentation or participant reported symptoms.
- Investigators should pay special attention to clinical signs related to previous serious illnesses.

**8.2.2. Vital Signs**

Vital signs will be measured, preferably in a seated position, after approximately 5-minutes rest and will include temperature, systolic and diastolic blood pressure, pulse, respiratory rate, and pulse oximetry. Results should be recorded on the appropriate eCRF.

**8.2.3. Weight and Height**

Weight should be measured throughout the study as indicated in the SoA. Coats and shoes should be removed prior to measurement. Height should be measured at baseline, preferably without shoes.

**8.2.4. Electrocardiograms**

[Redacted text block containing multiple lines of obscured content]

### 8.2.5. Echocardiograms/Multigated Acquisition Scans

### 8.2.6. Clinical Safety Laboratory Assessments

- Refer to [Appendix 2](#) for the list of clinical laboratory tests to be performed and the SoA (Section 1.3) for the timing and frequency.
- The investigator must review the laboratory report, document this review, and record any clinically relevant changes occurring during the study in the AE Section of the eCRF. The laboratory reports must be filed with the source documents. Clinically significant abnormal laboratory findings are those which are not associated with the underlying disease, unless judged by the investigator to be more severe than expected for the participant's condition.
- All laboratory tests with values considered clinically significantly abnormal during participation in the study or within 30 days after the last dose of study intervention should be repeated until the values return to normal or baseline or are no longer considered clinically significant by the investigator or Medical Monitor.
  - If such values do not return to normal/baseline within a period of time judged reasonable by the investigator, the etiology should be identified where possible, and the Sponsor notified.
  - All protocol-required laboratory assessments, as defined in Appendix 2, must be conducted in accordance with the SoA.
  - If laboratory values from non-protocol-specified laboratory assessments performed at the institution's local laboratory require a change in participant management or are

considered clinically significant by the investigator (eg, SAE, AE, or dose modification), then the results must be recorded in the eCRF.

#### 8.2.7.

[REDACTED]

#### 8.2.8.

[REDACTED]

### 8.3. Adverse Events and Serious Adverse Events

The definitions of an AE or SAE can be found in [Appendix 3](#).

AEs will be reported by the participant (or, when appropriate, by a caregiver, surrogate, or the participant's legally authorized representative).

The investigator and any qualified designees are responsible for detecting, documenting, and recording events that meet the definition of an AE or SAE and remain responsible for following up AEs that are serious, considered related to the study intervention or study procedures, or that caused the participant to discontinue the study intervention(s) ([Section 7](#)).

#### 8.3.1. Time Period and Frequency for Collecting AE and SAE Information

Monitoring and recording of AEs and SAEs will be conducted throughout the study. After the signing of the ICF, but prior to initiation of study intervention, only SAEs caused by a protocol-mandated intervention will be collected (eg, SAEs related to invasive procedures, such as biopsies or medication washout). Any medical occurrence that begins before the start of study intervention but after obtaining informed consent, and which is not considered an SAE caused by a protocol-mandated intervention, will be recorded on the Medical History/Current Medical Conditions Section of the eCRF not the AE section.

All AEs and SAEs will be collected from the start of intervention until the safety visit or EOT visit, whichever is later. Any SAE that is determined to be study-drug related (possibly, probably, or definitely related) will be followed to resolution or stabilization, is determined to be irreversible by the investigator, the participant is lost to follow-up, or it has been determined that the study treatment is not the cause of the AE/SAE, whichever occurs first. After this period,

investigators should report only SAEs that are thought to be related to RMC-4630, RMC-4630 and cobimetinib combination, or RMC-4630 and osimertinib combination. AE/SAE reporting will end after the participant initiates alternative cancer treatment.

All SAEs will be recorded and reported to the Sponsor or designee within 24 hours of investigator awareness, as indicated in Appendix 3. The investigator will submit any updated SAE data to the Sponsor within 24 hours of it being available.

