### 3. OBJECTIVES AND ENDPOINTS

#### 3.1. RMC-4630 and Cobimetinib Combination

Objectives	Endpoints

Primary
 

• To characterize the safety and tolerability of the combination of RMC-4630 and cobimetinib in participants with relapsed/refractory solid tumors

• To define the MTD and RP2D and schedules for the combination of RMC-4630 and cobimetinib in participants with relapsed/refractory solid tumors

	

• Incidence, nature, and severity of treatment emergent AEs and SAEs, graded according to the NCI CTCAE v5 for the combination of RMC-4630 and cobimetinib

• Incidence and nature of DLTs for the combination of RMC-4630 and cobimetinib

Secondary
 
[Redacted]
	
[Redacted]

Tertiary/Exploratory
 
[Redacted]
	
[Redacted]

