#### **4.1.4. Duration of Therapy**

Participants will be permitted to remain on-study therapy until disease progression per RECIST v1.1, unacceptable toxicity, or other criteria for withdrawal are met ([Section 7.1](#) and [Section 7.2](#)), or end of study ([Section 4.3](#)), whichever occurs first. Participants will return to the clinical site for an EOT visit within 30 days after last treatment dose. Alternatively, participants may withdraw from the study at any time with or without cause and will be encouraged for EOT evaluation.

After termination of treatment, participants will continue on study for long-term survival follow-up every 3 months ( $\pm 2$  weeks), unless they withdraw consent for further follow-up or end of study.

The anticipated duration of the study is approximately 3 years, including 2 years of enrollment and 1 year of follow-up visits.

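### Routine AE collection ends at a visit with no stated minimum time after last dose, so post-dose follow-up can differ between participants from about 0 to 30 days

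*Combined protocol and SAP*

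**What the plan says.** Section 8.3.1 sets the rule: "All AEs and SAEs will be collected from the start of intervention until the safety visit or EOT visit, whichever is later". After that point, "investigators should report only SAEs that are thought to be related to RMC-4630" or to either combination. A second stop applies throughout: "AE/SAE reporting will end after the participant initiates alternative cancer treatment".

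The visits are timed elsewhere. Section 4.1.4 (cobimetinib arm) states: "Participants will return to the clinical site for an EOT visit within 30 days after last treatment dose". Section 4.2.4 says the same for the osimertinib arm, and so does the synopsis. Section 7.1 puts both visits under one limit: "Participants who discontinue study treatment should complete the safety follow-up or EOT visit, within 30 days after the last treatment dose". Section 7.2 repeats that limit.

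The primary endpoint in Section 3.1 is "Incidence, nature, and severity of treatment emergent AEs and SAEs, graded according to the NCI CTCAE v5", and Section 3.2 mirrors it for osimertinib. Section 9 summarises discrete data as frequency and percentage, and Section 9.4.2 displays AEs and SAEs by combination dose level.

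Section 8.2.6 uses a different horizon for laboratory tests. Clinically significant abnormal values found during participation "or within 30 days after the last dose of study intervention should be repeated" until they settle.

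**The concern.** The end of AE collection is tied to a visit and not to a time since last dose. Taking the later of two visits gives a minimum follow-up only if at least one of them has a minimum day, and in the visible text neither does. An EOT visit held a few days after last dose complies with the plan and closes routine collection that day.

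What can be lost is specific: non-serious AEs of any grade, and SAEs judged unrelated, with onset after an early visit. The endpoint counts events whatever their relationship to study drug, so both belong in it. The visible text neither defines *treatment-emergent* by a number of days nor adjusts for exposure, so unequal tails pass straight into the percentages that are compared across dose levels. Those percentages are part of the evidence from which the sponsor sets the RP2D (Sections 4.1.1.3 and 4.2.1.3).

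**Working it through.** **Step 1. Post-dose tail allowed by the visible text.** The upper limit is 30 days (synopsis, 4.1.4, 4.2.4, 7.1, 7.2). No lower limit is stated. The tail *t* therefore lies between about 0 and 30 days. The full counting window is days on treatment *T* plus *t*.

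**Step 2. The plan's own AE figure.** Section 9.2 gives the chance of seeing at least one case of a specific AE among 144 participants as 76%, 95% and >99% for true incidences of 1%, 2% and 5%. The formula is 1 − (1 − p)^144:
- p = 1%: 76.5%
- p = 2%: 94.6% (0.9455)
- p = 5%: 99.9%

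The figures reproduce. Nothing in the sample-size text is wrong.

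**Step 3. Illustration of the effect of the tail.** The documents give no expected treatment duration and no hazard, so both are assumed here: *T* = 28, 56, 112 or 168 days, with constant hazard through treatment and tail. If an AE has incidence p over *T* + 30 days, the incidence counted with tail *t* is

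1 − (1 − p)^((T + t)/(T + 30)).

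Example: p = 20%, T = 28, t = 0 gives 1 − 0.8^(28/58) = 10.2%.

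| T (days, assumed) | Window, visit on day 0 vs day 30 | Ratio | 20% AE counted: day 0 | day 7 | day 14 |
|---|---|---|---|---|---|
| 28 | 28 vs 58 | 2.07 | 10.2% | 12.6% | 14.9% |
| 56 | 56 vs 86 | 1.54 | 13.5% | 15.1% | 16.6% |
| 112 | 112 vs 142 | 1.27 | 16.1% | 17.1% | 18.0% |
| 168 | 168 vs 198 | 1.18 | 17.2% | 17.9% | 18.5% |

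For an AE at 10% over *T* + 30 days, the day-0 column becomes 5.0%, 6.6%, 8.0% and 8.6%.

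**Step 4. Same illustration on the detection figure.** Take p = 1% over *T* + 30 days and put all 144 visits on day 0. For T = 28 the counted incidence is 1 − 0.99^(28/58) = 0.48%, and the detection probability falls from 76% to 50%. For T = 56, 112 and 168 it falls to 61%, 68% and 71%.

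Each column assumes that all visits fall on the same day. The day-0 results are the lower extreme; any mix of visit days from 0 to 30 lies between them and the full 30-day figures.

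**The case against.** The strongest reply is that the missing minimum may not be missing. Section 8 refers to the Schedule of Activities for the timing of procedures, and that schedule is redacted. Section 8.3.1 names two visits, and the schedule could give one of them a minimum day. The separate SAP announced in Section 9.4 may also define *treatment-emergent*. This stands: one can say only that the visible text has no minimum, not that the plan has none. The collection rule in 8.3.1 would still be clearer if it carried its own cut-off.

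Other safeguards also stand:
- Drug-related SAEs remain reportable after the visit until alternative therapy starts, and Section 8.3.3 follows them to resolution or stabilisation.
- AEs already recorded are followed through the last study visit, so an event that caused discontinuation is not lost.
- DLTs, which drive both escalation designs, use a 28-day Cycle 1 window. Table 15 keeps participants who stop for AEs in that window evaluable unless relationship is ruled out. For someone who stops in Cycle 1 and has an early EOT visit, the visible text does not say which window governs non-serious events, so the protection is large but not complete.

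A reader might infer that the whole AE window can be very short. It cannot be inferred in general: all time on treatment counts, and only the tail varies. A reader might also take the tail in isolation: if 20% had a new AE in the 30 days after last dose, a day-7 visit would capture 1 − 0.8^(7/30) = 5.1%, a shortfall of 14.9 points. That is a tail-only contrast on an assumed rate. The endpoint counts treatment plus tail, and a participant who already had the event on treatment is already counted.

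**Conclusion.** The point holds for the visible text and is limited to the post-dose tail. Routine capture of new non-serious AEs and unrelated SAEs can end anywhere from about day 0 to day 30 after last dose, and the primary AE and SAE percentages inherit that inequality.

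Its size cannot be computed from the documents. Under the assumed durations, the window ratio between a day-30 and a day-0 visit is about 2 for someone stopping after one cycle and about 1.2 after six. The loss in counted incidence is largest for short treatment and shrinks with longer treatment. Incidence of any AE is probably little affected: Section 2.3.1.2 reports that every patient in the cobimetinib monotherapy study had one. The exposure is in specific and late-onset events.

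It is tempting to add that the under-count is worst at toxic doses, because early stoppers would be seen early. This is possible, but the documents do not show it: nothing visible links visit day to dose level or to reason for stopping. The study is descriptive with no hypothesis test (Section 9.1), so the consequence is poorer comparability and some possible under-counting. No error in sample size or escalation rule follows.

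**What to change.** In Section 8.3.1, replace the visit-based end with a fixed one: collect all AEs and SAEs from first dose to 30 days after last dose, or to the start of new anticancer therapy if earlier. Thirty days is already the outer limit for the visit and the laboratory horizon in Section 8.2.6. Use the same cut-off to define *treatment-emergent* in Section 9.4.2 and the SAP. Add a day-30 telephone contact when the EOT visit is held earlier. Check the wording against the Schedule of Activities so that the two agree.

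The cost is a sentence or two, some telephone calls, and slightly higher reported AE incidences. The stop at new anticancer therapy is already in the protocol, and keeping it leaves some inequality for participants who move on quickly.
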